## 1.0 BACKGROUND/SIGNIFICANCE

Hidradenitis suppurativa (HS) is a chronic recurrent inflammatory disease of hair follicles primarily localized to the axillae, inframammary folds, suprapubic and inguinal skin, upper inner thighs, perineum, and buttocks. Early manifestations of HS include tender nodules that may progress into fluctuant abscesses. As the disease advances, recurrent inflammatory nodules and abscesses may develop permanent connecting dermal tracts (“tunnels”). Although the pathogenesis is poorly understood, HS is considered a disorder of follicular occlusion. The most recent estimate of HS prevalence in the United States is 0.10%; however, African Americans, females, and young adults are disproportionately affected. The median age of onset in females is 19 years and in males is 23 years. However, cases are reported in pediatric patients as early as 13 years old. Furthermore, HS is associated with a wide range of comorbidities, including cardiovascular, endocrine, gastrointestinal disorders, and psychiatric comorbidities, such as depression, anxiety, bipolar illness, and schizophrenia. There is not only greater disability and decreased quality of life compared to all other dermatologic conditions, but also the complexity and profound debilitation make management difficult and costly.

For more than 50 years, a standard therapy for acute HS flares has been the subcutaneous injection of triamcinolone, a fluorinated corticosteroid, into inflammatory nodules, abscesses and sinus tracts. The proposed mechanism involves activation of the glucocorticoid receptor, which blocks synthesis of leukotrienes and reduces the production of proinflammatory cytokines, including interleukin-1. Additionally, this therapy may inhibit cytotoxic T-cell activation.

Previous studies documented the efficacy of intralesional triamcinolone in decreasing erythema, edema, suppuration, and size of lesion, as well as patient-reported pain. Despite the proposed benefits of therapy, no standard effective dose has been established. Riis et al. conducted a prospective case series utilizing 10 mg/mL with the volume of injection based on patient lesion size, while Alvarez et al. performed a prospective open-label study injecting 40 mg/mL with a volume of 0.2-1 mL per fistulous tract.

At the Albert Einstein College of Medicine-Montefiore Hidradenitis Suppurativa Center (HSC), high-dose intralesional triamcinolone (20-40 mg/mL) is consistently used for hundreds of patients with inflammatory lesions. In an earlier retrospective review, it was reported that patients receiving high-dose intralesional triamcinolone (ILTAC) experienced improvement of disease state, quality of life, and overall satisfaction. Additionally, the majority of patients were interested in receiving future ILTAC injections as clinically indicated. Given the immense disease burden of HS, optimizing ILTAC dosing may dramatically improve medical management and quality of life (QOL) for our patients. We are seeking to determine optimal dosing by comparing response parameters of low dose (10 mg/mL) versus two concentrations of high-dose (20mg/mL and 40 mg/mL) triamcinolone injections in HS patients with active inflammatory lesions.

Due to the complex pathophysiology of HS, treatment poses a formidable challenge, incorporating antibiotics, anti-androgens and anti-inflammatory drugs. The latter includes systemic biologics and local corticosteroid injections. The standard corticosteroid used for acute nodules, abscesses, and draining sinus tracts reduces pain, redness, and swelling in 12- to

24-hours. Although ILTAC is considered a standard of care for acute flares in HS, studies documenting efficacy and side effect profile at varying doses are remarkably sparse.

Fajgenbaum et al. performed a double-blinded, randomized, placebo controlled trial comparing normal saline (NS), intralesional TAC 10 mg/mL (ILTAC-10), and intralesional TAC 40 mg/mL (ILTAC-40). There were no statistically significant differences between the varying concentrations and normal saline. However, the study was seriously under powered given the subject and lesion randomization parameters. Another major flaw in the study design was the randomization of lesions as opposed to participants. With this approach, systemic effects of the injection were not taken into account and likely obscured interpretation of the results.

Additionally, they did not compare to an intralesional TAC 20 mg/mL (ILTAC-20) group, which limits the insight into varying concentrations of high-dose triamcinolone injections. Perhaps, the most disastrous failing of the study design was limiting the injection volume to 0.1 mL regardless of lesion size. Pain reduction and patient satisfaction were evaluated from paper surveys mailed to participants at the conclusion of the study but the potential for recall bias undermined the data integrity. Markers of inflammation and side effects of ILTAC were not addressed. It is noteworthy that one prospective study showing the benefit of ILTAC-40 based the volume injected on lesion size, using up to 2 mL per lesion.

## 2.0 STUDY DESIGN

### a) Study Design

[figure not shown]
A double-blinded, randomized, placebo-controlled study examining the relative efficacy of ILTAC-10, ILTAC-20, and ILTAC-40 versus placebo for acute flares of HS in subjects with moderate to severe HS.

The duration of the study will be approximately 4 weeks for each enrolled patient and will include an initial screening/randomization/treatment visit and a 4-week follow-up period.

During the initial visit, subjects who meet the study's eligibility criteria will be randomized to receive either ILTAC-10, ILTAC-20, ILTAC-40, or normal saline (NS) placebo in a 1:1:1:1 ratio. The volume of ILTAC or NS administered is calculated based on the largest dimension of the HS lesion, which is measured by its greatest width in mm. For example, if a lesion is irregular in shape, measuring 22mm by 18mm, 22mm will be the largest dimension used for calculating volume. The administered volume (ml) is scaled by increments of 0.2ml, which corresponds to the HS lesion size, and ranges from 0.2ml to 2.0ml. The maximum volume of either ILTAC-10, ILTAC-20, ILTAC-40 or NS administered to any given HS lesion is 2.0ml.

**Figure 1.** Hidradenitis Suppurativa Lesion Size and Volume of administration of ILTAC-10, ILTAC-20, ILTAC-40, or normal saline placebo.

| HS lesion size (cm) | Volume (ml) |
|---------------------|-------------|
| 0.0 – 0.49          | 0.2         |
| 0.5 – 0.99          | 0.4         |
| 1.0 – 1.49          | 0.6         |
| 1.5 – 1.99          | 0.8         |
| 2.0 – 2.49          | 1.0         |
| 2.5 – 2.99          | 1.2         |
| 3.0 – 3.49          | 1.4         |
| 3.5 – 3.99          | 1.6         |
| 4.0 – 4.49          | 1.8         |
| 4.5 – 5.0           | 2.0         |

### Follow-up

The follow-up period will be of 4 weeks and will consist of 2 phone calls and 2 live visits, at week 2 and 4 after randomization.

A schedule of activities is shown in Section 5.0f.

### Study Objectives

#### *Aim 1*

- To compare the efficacy of ILTAC-10, ILTAC-20, and ILTAC-40 versus placebo for the treatment of acute HS flares.

#### *Aim 2*

- To investigate the side effect profile of ILTAC-10, ILTAC-20, and ILTAC-40 in the treatment of acute HS flares.

#### *Aim 3*

- To compare patient reported satisfaction and impact on quality of life regarding ILTAC-10, ILTAC-20, ILTAC-40 versus placebo for the treatment of acute HS flares.

### Hypothesis

Given the generally accepted anti-inflammatory property of fluorinated corticosteroids, it is anticipated that treatment with ILTAC will be superior to normal

saline for both acute HS flares, as well as patient reported outcome measures including HS-related pain and satisfaction after treatment. Additionally we expect a dose-dependent response when ILTAC-40 is compared to ILTAC-20 and ILTAC-10. Our preliminary findings suggest there will be no difference in subject side effect profile between the ILTAC and normal saline treatment arms.

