##### *Secondary Outcomes*

- Change from baseline in NRS pain scale at days 2, 6, and 14.
- Difference in change from baseline in NRS pain scale at days 2, 6, 14, and 28 between ILTAC-10, ILTAC-20, ILTAC-40.
- Change from baseline in HS-PGA score at week 2 and 4.
- Difference in change from baseline in HS-PGA score at week 2 and 4 between ILTAC-10, ILTAC-20, ILTAC-40.
- Change from baseline in objective markers of inflammation (c-reactive protein [CRP], erythrocyte sedimentation rate [ESR], and interleukin-6 [IL-6]) at week 2 and 4.

- Change from baseline in subjective markers of inflammation (erythema, edema, and suppuration) at week 2 and 4.
- Change from baseline in lesion size at week 2 and 4.
- Difference in change from baseline in lesion size at week 2 and 4 between ILTAC-10, ILTAC-20, ILTAC-40.
- Change from baseline in Patient-Reported Outcomes Measurement Information System (PROMIS) measure of physical functioning at days 2, 6, 14, and 28.
- Difference in change from baseline in PROMIS at days 2, 6, 14, and 28 between ILTAC-10, ILTAC-20, ILTAC-40.
- Proportion of subjects reporting side effects at days 2, 6, 14, and 28.
- Difference in proportion of subjects reporting side effects at days 2, 6, 14, and 28 between ILTAC-10, ILTAC-20, ILTAC-40.
- Baseline patient satisfaction.
- Change from baseline in patient satisfaction at days 2, 6, 14, and 28.
- Serum cortisol and ACTH levels at week 2 and 4.
- Change in serum cortisol and ACTH levels from week 2 to 4.

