#### c) Outcome Measures Pertaining to Each Aim

- *Aim 1:* To compare efficacy of ILTAC-10, ILTAC-20, and ILTAC-40 versus placebo, we will measure the change from baseline in pain, objective and subjective markers of inflammation, physical functioning, and lesion size as well as comparing these changes among the different treatment groups. Change from pain baseline will be quantified by comparison of the NRS pain scale across different treatment groups (Appendix B). Objective markers of inflammation include c-reactive protein (CRP), erythrocyte sedimentation rate (ESR), and interleukin-6 (IL-6), which will be obtained from chart review of standard of care initial, 2 week, and 4 week follow-up HS visit. Erythema and edema will be measured clinically based on a 5-point ordinal scale (Appendix E). Suppuration will be measured on a dichotomous scale, by the presence or absence of purulent drainage from the lesion. Physical functioning will be measured by change from baseline in the Patient-Reported Outcomes Measurement Information System (PROMIS) measure of physical functioning. Separate forms will be administered for adult and pediatric participants. A one point change, either positive (improvement) or negative (decline), will be considered clinically meaningful (Appendix F and Appendix G). Lesion size will be measured in centimeters at baseline and during the week 2 and 4 visit.

- *Aim 2:* Side effects of ILTAC-10, ILTAC-20, and ILTAC-40 that will be investigated include thinning/atrophy of the skin, acneiform lesions, capillary dilations, and dyschromia. Hypothalamic-pituitary-adrenal (HPA) axis suppression will be obtained through chart review of standard of care serum 8 AM cortisol and ACTH levels at week 2 and 4 follow-up HS visits. Self-evaluations will be conducted by the patient and documented via telephone interviews. Clinical-evaluations will be conducted at the follow-up visits.
- *Aim 3:* To measure the patient's satisfaction after treatment, we will compare the results from the satisfaction survey between the different treatment groups at baseline, day 2, day 6, week 2, and week 4. The patient satisfaction survey will address disease control, and response to injection (in terms of pain, drainage, and lesion size), and quality of life (Appendix D).

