## 7.0 DATA ANALYSIS

- a) Statistical Methods  
We will analyze the data from the study using an intention to treat approach. Categorical variables, including presence of side effects, drainage, and physical function, will be analyzed with chi square tests. Continuous variables, such as NRS pain scale, markers of inflammation, and lesion size, will be analyzed by T-test. Sensitivity analyses or exploratory analyses may be performed to examine the effect difference for race or gender. In the unlikely case patients do not receive the treatment they will still be randomized for analysis using a per protocol approach. All statistical tests will be 2-sided, with  $p < 0.05$  considered significant.
- b) There will be no interim analysis or early stopping of the study.
- c) Confounding and effect modification will be addressed by randomization of the subjects and blinding of both the investigators and the participants.
- d) If subjects are lost to follow up, they will be analyzed in the group to which they were initially randomized.

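### The plan expects no side-effect difference from saline, but its chi-square test has no margin or interval and cannot show that, and the aim and between-group outcome do not name saline

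*Combined protocol and SAP*

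**What the plan says.** Under Hypothesis (section 2.0), the protocol draws on earlier work to expect that "there will be no difference in subject side effect profile between the ILTAC and normal saline treatment arms". This is its only prediction about side effects, and it is made against saline.

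The places that should carry the prediction into the analysis are these:

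- **Aim 2** reads "To investigate the side effect profile of ILTAC-10, ILTAC-20, and ILTAC-40 in the treatment of acute HS flares". Aims 1 and 3 both name placebo as the comparator; Aim 2 does not.
- **Outcome Measures Pertaining to Each Aim (section 2.0 c)** repeats this under Aim 2: "Side effects of ILTAC-10, ILTAC-20, and ILTAC-40 that will be investigated include thinning/atrophy of the skin".
- **Secondary Outcomes** has a general item with no comparator, "Proportion of subjects reporting side effects at days 2, 6, 14, and 28", followed by one explicit between-group item, "Difference in proportion of subjects reporting side effects at days 2, 6, 14, and 28 between ILTAC-10, ILTAC-20, ILTAC-40".
- **Section 7.0 a)** gives the method: "Categorical variables, including presence of side effects, drainage, and physical function, will be analyzed with chi square tests". It does not say which arms are compared. All tests are two-sided with p<0.05 as the threshold.

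The documents contain no equivalence or non-inferiority margin, no confidence interval for side effects, no expected side-effect rate and no sample size for side effects. The figure of at least 30 per arm in section 3.0 b) comes from pain alone, saline against ILTAC-10.

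**The concern.** A chi-square test of this kind can give evidence that two proportions differ. When it fails to reject, it gives no evidence that they are the same, least of all in a small sample. With no margin or interval planned, the plan has no formal way to support its own prediction about side effects, and it does not say how a non-significant result will be described.

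The missing comparator adds to this. The prediction is against saline, but neither Aim 2 nor the explicit between-group outcome asks for that comparison.

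The consequence is practical. The background section describes evidence on side effects at different doses as sparse, section 3.0 b) foresees clinical use if pain falls substantially, and section 6.0 lists skin atrophy, dyschromia and HPA axis suppression as potential harms. A statement of no difference that rests on p>0.05 could carry more weight than the data allow.

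**Working it through.** **Inputs from the documents.** At least 30 per arm (section 3.0 b); 1:1:1:1 allocation (Randomization and Blinding); two-sided 0.05 and chi-square (section 7.0 a).

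**Inputs assumed.** All side-effect rates, because the documents give none. Saline rates of 0%, 5%, 10% and 20% are used below.

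**Step 1. Reproduce the plan's own figure.** Table 1, row ρ = 0.1: the SD of the change is √(1 + 1 − 2 × 0.1) = √1.8 = 1.342. A two-sided two-sample t-test with a difference of 1 and 30 per arm gives power 0.8102; Table 1 states 0.81021. The figure of 30 per arm is therefore right for pain under its own assumptions. It says nothing about side effects.

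**Step 2. Power of the planned test for side effects.** The method is exact enumeration: sum P(x)P(y) over all pairs of counts from two binomials (n = 30 each) for which the uncorrected chi-square has p<0.05.

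One case can be checked by hand. If the saline count is 0, then 3 of 30 on ILTAC gives χ² = 3.16 (p = 0.076) and 4 of 30 gives χ² = 4.29 (p = 0.038). With a true saline rate of 0%, power is therefore P(X ≥ 4). At a 10% ILTAC rate this is 1 − 0.647 = 0.353; at 20% it is 1 − 0.123 = 0.877.

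| Saline | ILTAC dose | Exact power, 30 v 30 |
|---|---|---|
| 10% | 20% | 19% |
| 5% | 15% | 26% |
| 0% | 10% | 35% |
| 5% | 20% | 45% |
| 10% | 30% | 50% |
| 0% | 15% | 68% |
| 5% | 30% | 78% |
| 0% | 20% | 88% |
| 5% | 35% | 88% |

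A true tripling from 5% to 15% would be non-significant about three times in four (1 − 0.26 = 0.74). An excess of 25 points from a 5% base would usually be found.

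**Step 3. Pooling the doses.** Comparing 90 ILTAC with 30 saline participants gives 27% for 5% vs 15% and 22% for 10% vs 20%. For excesses of this size, pooling hardly helps.

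**Step 4. What 30 per arm can say about a difference.** If both arms have the same rate p, the half-width of the 95% interval is 1.96 × √(2p(1 − p)/30):

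- p = 5%: 0.110, or 11 points
- p = 10%: 0.152, or 15 points
- p = 20%: 0.202, or 20 points

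With 0 of 30 events in one arm, the exact two-sided 95% upper limit for that arm's rate is 1 − 0.025^(1/30) = 11.6%.

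**Step 5. Is the saline comparison available?** Side effects are asked about at both phone contacts and both follow-up visits, and neither the visit descriptions nor the study calendar restricts this to the ILTAC arms. Saline data will therefore exist. What is missing is an explicit instruction to compare them.

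**The case against.** Several points on the other side are sound, and they limit the concern.

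- **No stated rule for p>0.05.** A reader might infer that the plan will treat a non-significant result as confirming its hypothesis. The documents do not say so. Section 7.0 a) defines only what counts as significant, and the hypothesis is worded as something that preliminary findings suggest. The gap is an interpretation left open.
- **Saline is not excluded.** A reader might infer that side effects are compared only between doses. Secondary Outcomes pairs a general item with a between-dose item for pain, HS-PGA, lesion size, PROMIS and side effects alike. The primary outcome also names no comparator, yet Aim 1 is plainly against placebo. The general side-effect item and the unrestricted chi-square sentence can both be read to include saline. What stands is that Aim 2 and the explicit between-group outcome do not name it.
- **False reassurance is not shown to be the likely result.** Power depends on rates that nobody has stated, and large excesses are detectable (Step 2). Testing at four visits with no stated adjustment also raises the chance of at least one significant result.
- **The chi-square is not all of Aim 2.** Cortisol and ACTH are continuous and would fall under the t-test in section 7.0 a), and adverse events are monitored separately. The point here concerns presence of side effects only.
- **Low power for safety is common** in a trial sized on an efficacy outcome, and 30 is a stated minimum. That is a fair reason not to ask for a larger trial. It does not justify a prediction of no difference without an analysis that can address it. No dropout allowance is stated either, and losses below 30 would widen the intervals.

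**Conclusion.** The concern holds in a limited form. The plan predicts no side-effect difference from saline and provides only a difference-seeking test, with no margin or interval, so a non-significant result could not support the prediction. The comparator also needs to be named in Aim 2 and in the between-group outcome; this is a specification gap and not an absence of data.

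Under assumed rates with 30 analysed per arm and one test at 0.05, an excess of 10 points is detected with 19% to 35% power in the scenarios shown (10% vs 20%, 5% vs 15%, 0% vs 10%). A 20-point excess from a zero base is detected with 88% power, and a 25-point excess from a 5% base with 78%. With both arms at 10%, the data would leave differences of up to about 15 points in either direction open. Small to moderate excesses would often be missed, while large ones would probably be seen.

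The documents do not support the stronger conclusions that the plan commits to reading p>0.05 as equality, or that a falsely reassuring result is to be expected. This should be corrected before analysis; it does not threaten the primary pain comparison.

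**What to change.** 1. Name saline as a comparator in Aim 2, in the matching text of section 2.0 c), and in the between-group side-effect item under Secondary Outcomes.
2. In section 7.0 a), report each ILTAC dose minus saline as a risk difference with a 95% confidence interval at days 2, 6, 14 and 28. Use an exact or score method, because counts may be sparse. Any side effect through day 28 could be added as an optional summary; it is not a listed outcome now.
3. Reword the sentence under Hypothesis as an expectation to be estimated.
4. State that p>0.05 will not be reported as no difference, and that conclusions will rest on the interval.

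The cost is wording in the protocol and analysis section. No participants, visits or procedures are added. The small downside is that the safety conclusion will be less favourable than a plain statement of no difference, because wide intervals will be visible.

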#### Target population and recruitment methods

The target population will include patients over the age of 13 receiving care at the HSC for mild to advanced HS disease experiencing an acute flare. Patients will be recruited by the PI and study personnel (recruitment strategies are detailed in section 4).

#### Inclusion Criteria

- Age > 13 years old.
- Subject must voluntarily sign and date an informed consent, approved by an independent ethics committee / institutional review board.
- Subject is willing to comply with the procedures in this protocol.
- The subject must be diagnosed with HS and receiving care at HSC
- Subjects with Hidradenitis Suppurativa Physician Global Assessment (HS-PGA) score between 2 and 5 (Appendix A).
- The subject must have an inflamed nodule or abscess at the time of enrollment.

#### Exclusion Criteria

- The subject has an HS-PGA score of 0 or 1
- The subject has received ILTAC less than 8 days prior to the initial visit.
- The subject does not have capacity to consent to the study.
- The subject has taken systemic steroids at least 4 weeks prior to the time of enrollment.
- The subject has a known allergy or history of adverse reaction to steroids.
- The subject is pregnant.
- Subjects who have received a biologic therapy two weeks before and during the study period.

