Participant eligibility will be assessed according to inclusion and exclusion criteria in 2.0a. A member of the study team will describe the study and answer any of the participant's questions. The participant will then be consented and enrolled. The initial visit and all subsequent visits will include documentation of NRS pain scale (Appendix B), HS-PGA, Hurley Stage (Appendix C), clinical markers of inflammation, and lesion size (as specified in our standard approach to care. Photographs of the lesions will be obtained. The study personnel will administer a patient satisfaction survey and the PROMIS questionnaire, which will take 15 minutes to complete (Appendix D and Appendix F [or Appendix G if pediatric]). Chart review will record demographic information (age, gender, race, ethnicity, smoking status, and BMI) and complete blood count (CBC), basic metabolic profile (BMP), liver function tests (LFT), erythrocyte sedimentation rate (ESR), c-reactive protein (CRP), and interleukin-6 (IL-6). The lab work is a standard of care at the HSC independent of research objectives. The patient will receive an injection, not to exceed 2 mL per anatomic area, in up to 3 anatomic areas (total of 3mL). The patient will be counseled regarding potential side-effects of the treatment (Appendix H) and asked to monitor accordingly. No other changes to the patient's HS medication regimen will be made for the duration of the study.

- Phone Contact 1 (2-day post-treatment)

Since triamcinolone has a half-life of 18 to 36 hours, the initial patient follow-up will be a phone call at 2 days post-injection, lasting 15 minutes. Study personnel will administer a patient satisfaction survey and the PROMIS questionnaire (Appendix D, and Appendix F [or Appendix G if pediatric]). Additionally, patients will be asked if they experienced any side effects, including thinning/atrophy of skin, acneiform lesions, capillary dilation, and/or dyschromia.

- Phone Contact 2 (6 days post-injection)

This 15 minute phone call will be 6 days post-injection and will involve administering the patient satisfaction survey, the PROMIS questionnaire, and questions about side effects.

- Visit 2 (2 weeks post-injection)

- The initial screening visit examination will be repeated at week 2. Additionally, the patient will be asked to identify side effects. A patient

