### 3.0 STUDY POPULATION

- a) Study Population: The study population includes patients >13 years old with HS by a physician. All patients with HS-PGA greater than 2 will be included, regardless of comorbidities.
- b) Sample Size/Power Calculation: The primary outcome of our trial is a reduction in pain measures before and after treatment. We will have 4 groups: normal saline, ILTAC-10, ILTAC-20, and ILTAC-40. Of importance, these ILTAC doses are currently used for HS flares and are standard treatment for other dermatologic conditions, such as keloids. To estimate the sample size needed in each arm, we assumed that the pain score in our patients is normally distributed. The mean difference in pain score between normal saline and ILTAC-10 is estimated to be 1, with a standard deviation of 1, at baseline and also two days later, as is consistent with our clinical experience. We also assumed a range of correlations (0.1-0.9) that may be observed for a patient's pain score at the multiple follow-up points. When comparing normal saline and ILTAC-10, the most conservative of the treatment arms in terms of pain change, it is shown that at least 30 participants per arm are required to detect the anticipated effects (see Table 1 below for power calculations). Additionally, given that we expect to see a greater reduction in pain with ILTAC-20 and ILTAC-40, we will be more than sufficiently powered to detect the large pain reductions anticipated in the ILTAC-20 and ILTAC-40 groups. This conservative approach allows for the detection of a clinically meaningful change, as any substantial reduction in pain would result in clinical utilization of ILTAC.

**Table 1.** Tests for Two Groups of Pre-Post Scores. Numeric Results for Comparing Mean Change in a Repeated Measures Design. Null Hypothesis:  $\delta = 0$ . Alternative Hypothesis:  $\delta \neq 0$ . Results assuming a t-test.

| Target Power | Actual Power | N1 | N2 | N  | $\delta$ | $\sigma(T1)$ | $\sigma(T2)$ | $\rho$ | $\sigma(Diff)$ | Alpha |
|--------------|--------------|----|----|----|----------|--------------|--------------|--------|----------------|-------|
| 0.8          | 0.81021      | 30 | 30 | 60 | 1        | 1            | 1            | 0.1    | 1.342          | 0.05  |
| 0.8          | 0.81347      | 27 | 27 | 54 | 1        | 1            | 1            | 0.2    | 1.265          | 0.05  |

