## 4.0 PARTICIPANT RECRUITMENT

- Those receiving care through the HSC at Montefiore Medical Center will be invited to enroll in the trial. It is estimated that the research team will have the capacity to screen and enroll 5 new patients per clinic. The day prior to each clinic, research personnel will use a random number generator to identify 8 potentially eligible patients based on inclusion/exclusion criteria, considering refusals or ineligibility, during the screening. After obtaining informed consent, patients will be enrolled in the study.
- We will register our study on <https://clinicaltrials.gov>.
- It will be explained that treatment will not be different for patients who do not wish to enroll in the study. Study participation is completely voluntary, and patients can choose to withdraw at any time.
- Patients privacy will be protected by assigning each participant a unique identifier for any analysis (see below for details).

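### As worded, the systemic-steroid exclusion bars use four or more weeks before enrolment and admits patients whose only use was within the last four weeks; the period intended is not stated

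*Combined protocol and SAP*

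**What the plan says.** The Exclusion Criteria in Section 2.0 a) contain this line: "The subject has taken systemic steroids at least 4 weeks prior to the time of enrollment". The list in Section 3.0 repeats it word for word, so neither list corrects the other.

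Two other lines in the same lists deal with prior treatment. The one on ILTAC reads: "The subject has received ILTAC less than 8 days prior to the initial visit". The one on biologics refers to the two weeks leading up to the study and to the study itself.

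The lists are operative. Section 2.0 b), Visit 1, states: "Participant eligibility will be assessed according to inclusion and exclusion criteria in 2.0a". Section 4.0 applies them earlier, on the day before clinic, when "research personnel will use a random number generator to identify 8 potentially eligible patients based on inclusion/exclusion criteria".

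The outcomes that prior steroid exposure could touch include pain on the NRS (primary, at week 4), "Change from baseline in objective markers of inflammation" (CRP, ESR and IL-6) and "Serum cortisol and ACTH levels at week 2 and 4". The laboratory tests listed for Visit 1 do not include cortisol or ACTH; those listed for weeks 2 and 4 do.

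**The concern.** An exclusion for prior treatment normally keeps out patients in whom that treatment may still be acting. As worded, this one does the reverse. It removes patients on account of remote use, however long ago, and lets in patients whose only use was recent.

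The plan expects corticosteroid to reduce inflammation and pain (Section 1.0) and names suppression of the hypothalamic-pituitary-adrenal (HPA) axis as a possible side effect of the injection (Section 6.0). If systemic steroids act in the same direction, which is an assumption but a modest one, recent use could do two things:

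- It could disturb baseline and follow-up values of pain and the inflammation markers, which adds variability to the changes being compared.
- It could leave a low cortisol or ACTH value at week 2 or 4 without a clear cause in an individual patient, because no pre-treatment value is listed for comparison. HPA-axis suppression is one of the Aim 2 safety measures.

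In the other direction, a literal screener would turn away patients for steroid use years earlier, for no reason that the protocol gives.

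**Working it through.** No sample size, power or alpha figure bears on this point, so there is no figure in the plan to reproduce. The check applies each rule to the time since use.

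**Inputs.** Let d be the number of days before enrolment on which the drug was used, with 4 weeks = 28 days. Consent, enrolment and treatment all fall at the initial visit (Section 2.0), so the ILTAC and steroid lines count back from the same day.

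- Steroid line as worded (both lists): exclude if any use has d ≥ 28.
- Steroid line read as a recent-use washout (not written anywhere; used for comparison): exclude if any use has d < 28.
- ILTAC line as worded (both lists): exclude if any use has d < 8.

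**Result for a single use on day d** (in the last column, d is the day of the ILTAC injection):

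| d (days) | Steroid line as worded | Steroid line as a washout | ILTAC line as worded |
|---|---|---|---|
| 1, 7 | admit | exclude | exclude |
| 8, 14, 27 | admit | exclude | admit |
| 28, 29, 60, 365, 3650 | exclude | admit | admit |

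Three things follow.

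1. For a single use, d ≥ 28 and d < 28 are complements, so the literal and washout readings give opposite decisions on every date. Use on day 7 is admitted by one and excluded by the other; use on day 3650, about ten years earlier, is the reverse.
2. The steroid line as worded excludes above its threshold, and the ILTAC line excludes below its own. They run in opposite directions.
3. The restriction to patients whose only use was recent is needed. A patient with use on both day 7 and day 60 is excluded by the literal rule because 60 ≥ 28, and by the washout reading because 7 < 28.

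**Does other text settle it?** The repeated list does not, since its wording is identical. The Visit 1 and recruitment text apply the criteria without explaining them. Visit 1 also says "No other changes to the patient's HS medication regimen will be made for the duration of the study", but that governs changes to HS medication during the study and not what was taken before it. No other text bars systemic steroid use in the four weeks before enrolment.

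**The case against.** The strongest reply is that everyone will understand what was meant. The literal rule is implausible in a steroid trial, the ILTAC and biologic lines both look to recent exposure, and one centre's team does the screening. On this view the line is a loosely phrased washout and will be applied as one.

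Much of that stands. The neighbouring lines do make a reversed washout the likeliest explanation, and nothing shows that staff would read the line literally. But the inference has to be supplied by the reader. The sentence says the opposite, it appears twice, and an eligibility decision that follows the protocol exactly would differ from one that follows its probable intent.

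A second reply is that the ILTAC and steroid lines cover different exposures, local and systemic, so nothing obliges them to point the same way. That is correct. A reader might infer that the two lines contradict each other; they do not. The comparison is evidence of what was intended and no more.

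A third reply is that the consequence is thin, because randomisation balances prior steroid use across arms on average. This also stands. A reader might infer that the week 4 pain comparison is biased, or that recently exposed patients will be enrolled in number. The documents support neither: they give no count of such patients and no indication of how staff apply the line.

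**Conclusion.** The point holds as a defect in an operative eligibility rule. As worded, the systemic-steroid exclusion bars use 28 or more days before enrolment without limit and admits patients whose only use was more recent. It probably reverses a recent-use washout, but the protocol does not say so and nothing else in it covers recent use.

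The size of the effect cannot be given. The number of patients with recent systemic steroid use is not in the documents, and none is assumed here. What can be said is that literal application could add noise to pain and to CRP, ESR and IL-6, and could weaken the reading of week 2 and 4 cortisol and ACTH in individual patients. This rests on two assumptions: that recent systemic steroids affect these measures, and that some screened patients have had them. Average balance between arms is protected by randomisation, and no bias in the primary outcome is shown. The line should be corrected, but it does not undermine the trial's main comparison.

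**What to change.** The sponsor should reconcile the systemic-steroid line with the other prior-treatment exclusions and state, in identical and unambiguous words in Sections 2.0 and 3.0, which period before enrolment is excluded. The length of that period is for the sponsor to decide; this review proposes none.

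The cost is one sentence reworded in two places in a protocol amendment. Sample size, visits and analysis are unchanged. Recording the date of last systemic steroid use at Visit 1 would let the rule be audited, but it is optional.
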